**Document Date: December 15, 2016**

**NCT01504438**

## Prospective Randomized Evaluation Of A Two And Three Piece Total Ankle Replacement

**Purpose of the Study** – Randomized study to prospectively compare and evaluate the functional outcome and patient satisfaction of total ankle replacements for tibio-talar osteoarthritis using either the STAR or Salto-Talaris prothesis.

**Background & Significance** – The primary articulation of the ankle joint is between the tibia and talus. This joint is subjected to extreme forces during daily activity and therefore is susceptible to the development of osteoarthritis. Severe osteoarthritis of the ankle is treated either by joint fusion or replacement. Traditionally, most orthopaedic surgeons have opted for joint fusion over replacement because of the high failure rates and poor technology of total ankle replacements. However, newer total ankle replacements are being introduced with better results, largely due to borrowed technology from the tried and true fields of total hip and knee replacement. Therefore, more surgeons are opting for ankle replacement to preserve ankle motion and prevent adjacent joint osteoarthritis often seen with ankle joint fusion. In the US at present time, there is a single 3 piece ankle prothesis (STAR) and several 2 piece (Salto-Talaris, InBone, Agility) approved for use. Currently there is debate in the orthopaedic community about whether a 2 piece or 3 piece ankle replacement is superior in terms of longevity, satisfaction, and function. This study will evaluate patient satisfaction and functional outcome of total ankle replacement for ankle osteoarthritis by one of two different currently available and approved ankle prothesis, the STAR and the Salto-Talaris.

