**Design & Procedures** – Adult patients (age > 18 years) who have severe osteoarthritis of the ankle joint significant enough to be treated with a total ankle replacement as determined by Drs. [name], [name], or [name] with the aid of the physical exam and routine radiography, treated at Duke University Medical Center will be asked to participate in this study. After routine surgical counseling by Drs. [name], [name], [name] or [name], those patients meeting the inclusion criteria will be asked to participate in this study by their attending physician. The consent form will be administered in the clinic. No PHI will be collected prior to consent. If a patient chooses to participate, they will be asked to sign the consent form and will be asked to complete the following patient outcome questionnaires (attached): Visual Analog Pain Scale, Short-form 36, AOFAS hind foot score, a Short Musculoskeletal Function Assessment questionnaire and FADI. Also at this time patients will be randomly assigned to receive either the STAR or Salto-Talaris ankle prosthesis at the time of their surgery. There will be 80 individual, sealed, opaque sequentially numbered envelopes containing the randomization of either ankle prosthesis (40 of each implant). The patient will then undergo surgery as scheduled at a later date. Participants will be in the study a total of ten years.

Following surgery, the patient will present for routine follow-up appointments. At the six month, one year, two year, three year visit and every year thereafter, the patients participating in the study will be asked to complete the previously mentioned outcome questionnaires. These are all normal follow-up visit time points; the patients will not be asked to return to clinic for any additional visits that would not be routine. At each visit, the patient will also receive plain x-rays. Plain x-rays are part of routine follow-up and not additional tests for this study.

The study will proceed until a minimum of ten-year follow-up is achieved for all patients. We will leave the ten year window open for all subjects until the last subject has finished their ten year time point. This will ensure that all subjects will have an appropriate time span in order to return for their standard of care visit.

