**Data Analysis & Statistical Considerations** – The data will be summarized using routine descriptive statistics. The following clinical outcome parameters will be analyzed using a series of 2X4 between subject repeated measures ANOVAs, with Tukey post hoc testing to determine statistically significant differences. The 2 X 4 ANOVA will be comparing the 2 groups (Salto Talaris and STAR implants) and the five time points of interest (pre-op, 6 months, 1 year, 2 years, and 3 years following surgery). The clinical outcome variables of interest will be the visual analog pain scale, foot and ankle disability index, the SF-36, the AOFAS hind foot score, and the short form musculoskeletal assessment. In addition, radiographic measurements will be collected on the radiographs that are available in the patients' medical record at each of the pre and post-operative time points. Monitoring of data will not be done until the final analysis after all data is collected. A p-value less than 0.05 will be used as the level of statistical significance for this study.

**Data & Safety Monitoring** - Monitoring data for safety is a function of the PI and study team. The PI will be responsible for review and sign off on all adverse events and/or problems as they occur and report adverse events and/or problems as required by HRPP policies to the IRB.

**Data storage & confidentiality** – The principal investigator and co-investigators will collect data in a computerized database using a commercially available database program. During collection, data will be indexed by the patient's medical record number. After data collection, a case number will be assigned to the data, and the medical record number (the only identifying data collected) will be stripped from the database. The code linking medical record number to case number will be kept in a locked file with access limited to the primary investigator. When the study is complete the code linking medical record numbers to case numbers will be destroyed. During data collection and review protected health information will be available only to the principal investigator and co-investigators and will not be reused or disclosed to any other person or entity, except as required by law, for authorized oversight of the research study.

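### Scores are scheduled at 12 points to year 10, but the only planned test of the implants covers five points to year 3, is labelled 2X4, and has no rule for missed visits

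*Combined protocol and SAP*

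**What the plan says.** **Collection.** Design & Procedures has patients complete five instruments at consent: a pain scale, the SF-36, the AOFAS score, the short musculoskeletal assessment and the FADI. After surgery the schedule is "At the six month, one year, two year, three year visit and every year thereafter", when patients "will be asked to complete the previously mentioned outcome questionnaires". On duration: "Participants will be in the study a total of ten years". On the last visit: "We will leave the ten year window open for all subjects until the last subject has finished their ten year time point". The text after Design & Procedures adds that subjects are being asked for permission to carry on to the 10-year point, and that a letter about this change is mailed to them.

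**Purpose.** The stated aim is to "compare and evaluate the functional outcome and patient satisfaction of total ankle replacements". No time horizon is attached to it.

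**Analysis.** Data Analysis & Statistical Considerations says "The data will be summarized using routine descriptive statistics" and then plans "a series of 2X4 between subject repeated measures ANOVAs" with Tukey post hoc tests, comparing the two implants over "the five time points of interest (pre-op, 6 months, 1 year, 2 years, and 3 years following surgery". This is one type of analysis, repeated for each of the five instruments. The final analysis is to follow the completion of data collection. The section does not say what happens to a patient with a missing score.

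**The concern.** The analysis section stops at year 3 while collection runs to year 10. Nothing says that the later scores are meant to be descriptive only. If that is left open, any comparison of the implants at years 4 to 10 has its model, time point and instrument chosen after the data are in. Those years are the reason for asking patients to extend their follow-up.

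Two further gaps sit in the same paragraph. The model label does not match its own list of time points. And the method named normally needs a complete set of visits from each patient, while follow-up relies on routine clinic attendance and the plan has no rule for a missed visit. At stake are the precision of the 3-year comparison and the standing of any ten-year one.

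**Working it through.** **1. Time points (Design & Procedures against Data Analysis).**
- Scheduled: pre-op (1) + 6 months (1) + years 1 to 10 (10) = 12.
- In the ANOVA: pre-op, 6 months, years 1, 2 and 3 = 5.
- With no planned test: 12 − 5 = 7, that is 7/12 = 58% of all assessments, or 7/11 = 64% of the post-operative ones.

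**2. The 2X4 label.** Four is obtained only by leaving out pre-op, but the plan lists pre-op among the points compared. The listed design is 2x5, with 4 degrees of freedom for time and for implant-by-time instead of 3.

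**3. Patients kept by a complete-visit ANOVA over the five points.** Assumptions: pre-op is always observed, and average missingness per post-operative visit is m = 5%, 10% or 20%.
- Independent misses: kept = (1 − m)^4 = 0.95^4, 0.90^4, 0.80^4 = 0.815, 0.656, 0.410.
- Permanent dropout: a constant hazard h per visit is chosen so that the mean of 1 − (1 − h)^k over k = 1 to 4 equals m. This gives h = 0.0204, 0.0417, 0.0873 and kept = (1 − h)^4 = 0.921, 0.843, 0.694.

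**4. Half-width of the 95% CI for the year-3 difference, in SD units.** n = 50 per arm, from the enrolment target in the recruitment section.
- No loss: 1.96 × √(2/50) = 0.392.
- Complete-case: 1.96 × √(2/(50 × kept)). For example, 1.96 × √(2/(50 × 0.410)) = 0.61.
- Mixed model: 1.96 × √(2V/50), where V/50 is the variance of one arm's year-3 mean. V comes from the average information matrix over simulated missingness patterns, with a separate mean for each implant and time. Assumed correlation is either constant (0.5 or 0.7) or decaying (0.5 or 0.7 per year).

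| Pattern | m | Kept | Complete-case | Mixed model |
|---|---|---|---|---|
| Independent | 5% | 81% | 0.43 | 0.40 |
| Independent | 10% | 66% | 0.48 | 0.40–0.41 |
| Independent | 20% | 41% | 0.61 | 0.41–0.43 |
| Dropout | 5% | 92% | 0.41 | 0.40–0.41 |
| Dropout | 10% | 84% | 0.43 | 0.41–0.42 |
| Dropout | 20% | 69% | 0.47 | 0.43–0.46 |

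**5. What a year-10 comparison could deliver.** The same mixed-model calculation over 11 post-operative visits gives these half-widths across all scenarios:
- 50 per arm: about 0.40–0.48 SD (no loss: 0.39).
- 40 per arm, the number of envelopes per implant in Design & Procedures: about 0.44–0.54 SD (no loss: 0.44).

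The upper ends come from 20% dropout with decaying correlation. With constant correlation the ranges stop at 0.45 and 0.50. Patients who do not re-consent to the longer follow-up are not in these figures and would widen the interval further.

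**6. Which scores reach year 10.** The standard-of-care questionnaire set described after Design & Procedures shares four instruments with the analysis section. It lists the Foot and Ankle Outcome Score where the other two sections have the FADI.

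**The case against.** The ten-year horizon looks, at least for patients already consented, like a later extension. On that view the five-point analysis is the trial's intended comparison, and the purpose promises no ten-year result. That stands, and it limits the point: the analysis section was either not updated for the extension or does not say that the late scores are descriptive.

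The case for replacing the ANOVA is also thin if missingness is mostly dropout, as the table shows, and the documents support no particular rate or pattern. That stands too. The mislabelled dimension is editorial, because the five points are named.

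Four stronger readings are tempting and are not supported:
- *Years 4 to 10 are discarded.* The descriptive summaries may cover them. What is missing is a planned comparison.
- *The ANOVA will lose most of the patients.* That needs about 20% scattered misses, which is an assumption.
- *The open ten-year window, or the use of available radiographs, already deals with missed visits.* The first governs when one visit may occur, and the second concerns radiographs only.
- *Deferring the analysis guarantees that nobody has seen comparative results.* The documents do not establish this. They describe no blinding and give no cut-off for the 3-year comparison.

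**Conclusion.** The point holds in this form: the planned analysis does not match the planned follow-up. Seven of 12 scheduled assessments have no inferential comparison and no statement that this is intended. The model label contradicts its own list, and missed visits have no rule. These follow directly from the text.

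The size of the precision loss is conditional. At year 3 with 50 per arm, a complete-visit ANOVA gives half-widths of 0.43–0.61 SD under independent misses against about 0.40–0.43 SD for a mixed model. Under pure dropout the gain is at most a few hundredths of an SD. A ten-year comparison would remain informative under the assumed rates, but its precision depends on how correlation behaves over time and on how many patients re-consent.

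This should be corrected, but it does not invalidate the 3-year comparison.

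**What to change.** In Data Analysis & Statistical Considerations:

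(a) Correct the label to 2x5.

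(b) Replace the ANOVA with a linear mixed model for each score, with implant, time and implant-by-time, using all available scores. State that it assumes missed scores are explained by observed ones (missing at random). Keep the comparison through year 3. Add a pre-specified secondary comparison through year 10, reported as between-implant differences with 95% CIs and no further significance claims. Report by implant, at each year, the number assessed and the number re-consented.

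(c) State the data cut-off for the 3-year comparison: when the last patient passes that visit, or only once ten-year data are complete, about 10 − 3 = 7 years later.

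(d) Confirm that the FADI is collected through year 10, and limit the ten-year comparison to scores actually collected.

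Cost: wording and a little more analysis work, with no new visits or patients. The mixed model does not remove bias if missingness depends on unseen scores. Releasing 3-year results early would make comparative results known during later follow-up.

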All patients who receive a total ankle replacement at Duke is asked to complete a set of questionnaires (Visual Analog Scale, Short Musculoskeletal Function Assessment, Short Form-36 Health Survey, Foot and Ankle Outcome Score Questionnaire, AOFAS Ankle-Hindfoot Scale) as part of the Duke Orthopaedics Foot and Ankle physicians' standard of care. We will ask subjects permission to use these questionnaires that have been collected from them since their randomized TAR surgery. We are also asking subjects permission to release their de-identified study information to orthopaedic equipment manufacturers, and to continue their follow-up to their 10-year post-operative time point. A letter will be mailed to all subjects explaining the change. This letter is explained in the Consent Process section. Drs. [name], [name], [name], [name] will only be recruiting their own patients

**Subject identification, recruitment, and compensation**- Inclusion/ Exclusion criteria: Adult patients (age > 18 years) who will benefit from a total ankle replacement, as determined by Drs. [name], [name], [name] or [name], with the aid of the physical exam and routine radiography treated at Duke University Medical Center and who have no medical conditions that would represent contraindications to surgery or anesthesia will be

asked to participate in this study. The only excluded patients will be those who do not choose to participate in this study, have a weight greater than 230lbs, or do not meet the minimum age of 18 years. Drs. [name], [name], or [name] will only be recruiting their own patients. Drs. [name], [name], [name] or [name] will not personally obtain consent due to a conflict of interest related to their consulting relationship with Tornier Inc and SBI Inc. Approximately 100 DUHS patients will be recruited to undergo either a STAR or Salto-Talaris Total Ankle Replacement. Study enrollment will be complete once 50 of each cohort have been treated. There is no compensation associated with participation in this study.

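### Five unranked instruments are each tested at p<0.05 with no primary instrument and no deciding implant contrast, so the chance of a false-positive group test is about 10% to 23% rather than 5%

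*Combined protocol and SAP*

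**What the plan says.** All of this is in the combined protocol and SAP. Data Analysis & Statistical Considerations lists the instruments in a single unranked sentence that begins "The clinical outcome variables of interest will be the visual analog pain scale, foot and ankle disability index, the SF-36" and goes on to AOFAS and SMFA. Each gets its own group-by-time repeated measures ANOVA, "with Tukey post hoc testing to determine statistically significant differences". The layout is labelled 2 x 4, yet the same section counts "the five time points of interest (pre-op, 6 months, 1 year, 2 years, and 3 years following surgery"), which is five levels. The section sets one significance level: "A p-value less than 0.05 will be used as the level of statistical significance for this study". No adjustment across instruments is described.

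Purpose of the Study states a randomized comparison of function and satisfaction. It names no primary outcome and does not call the comparison exploratory.

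On data access, the analysis section says "Monitoring of data will not be done until the final analysis after all data is collected". Design & Procedures says of the study follow-up visits that "the patients participating in the study will be asked to complete the previously mentioned outcome questionnaires". It also gives a standard-of-care list that includes "Short Form-36 Health Survey, Foot and Ankle Outcome Score Questionnaire, AOFAS Ankle-Hindfoot Scale" but not FADI.

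**The concern.** Two choices are left open, and both affect the error rate. The first is which instrument carries the conclusion. The second is which test on that instrument does so: the group main effect, the group-by-time interaction, or a Tukey comparison between cell means. With every combination judged at 0.05, a reader of the final report cannot tell whether a significant result was the planned test or the best of several. The nominal 5% then does not describe the risk of a false implant claim.

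The unnamed term also affects what is estimated. The baseline questionnaires are completed before surgery, so no implant effect can exist at that point. Whether pre-op is a level of the ANOVA therefore changes what the group term measures, and the conflict between the 2 x 4 label and the five listed time points leaves this undetermined.

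**Working it through.** The plan gives no power calculation or study-wise error rate, so there is no figure of its own to reproduce.

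**Inputs from the document:** alpha 0.05, taken as two-sided because an F test is non-directional; five instruments, counted as one score each; two implants; 50 per arm (Subject identification, recruitment, and compensation) or 40 per arm (the envelopes in Design & Procedures).

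**Assumptions:** equal correlation r between instruments, equal within-patient correlation rho between visits, complete data.

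**Step 1. Any of five group tests significant, implants equal.**
- At r = 0: 1 - 0.95^5 = 0.226.
- At r > 0: 1 - E{[Phi((1.96 - sqrt(r)U)/sqrt(1-r)) - Phi((-1.96 - sqrt(r)U)/sqrt(1-r))]^5}, with U standard normal.
- Results: 20.9% (r = 0.3), 18.3% (0.5), 14.8% (0.7), 12.7% (0.8), 10.2% (0.9).
- Simulated t tests at r = 0, 0.5 and 0.9 give 22.5%, 18.3% and 10.3% at 40 per arm, and 22.7%, 18.6% and 10.3% at 50. Arm size hardly matters.

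**Step 2. Group-by-time may also count.** Simulated ANOVAs (6,000 trials, five visits, rho = 0.5, 50 per arm) give 40.7%, 33.4%, 28.7% and 19.9% at r = 0, 0.5, 0.7 and 0.9. Tukey comparisons, SF-36 subscales and radiographic measurements are not counted.

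**Step 3. What the group term estimates.** Take a constant post-operative difference d.
- Pre-op as a level: (0 + d + d + d + d)/5 = 0.8d.
- Four post-operative levels: (d + d + d + d)/4 = d. There is no dilution, but the pre-op value is unused.

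**Step 4. Power for a steady difference** (0.5 SD at every post-operative visit, one instrument, n = 50 per arm). In SD units:
- Group term, five levels: SE = sqrt[(1+4rho)/5 x 2/n]. At rho = 0.5, SE = 0.155 and 0.40/0.155 = 2.58.
- Group term, four post-operative levels: SE = sqrt[(1+3rho)/4 x 2/n] = 0.158 and 0.50/0.158 = 3.16.
- Group-by-time: noncentrality = (n/2) x sum of squared deviations/(1-rho) = 25 x 0.20/0.5 = 10, on 4 and 392 df.
- Adjusted post-operative average: SE = sqrt{[(1+3rho)/4 - rho^2] x 2/n} = 0.122 and 0.50/0.122 = 4.1.
- Adjusted 3-year contrast: SE = sqrt[(1-rho^2) x 2/n] = 0.173 and 0.50/0.173 = 2.89.

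| Test | rho 0.3 | rho 0.5 | rho 0.7 |
|---|---|---|---|
| Group term, five levels | 85% | 72% | 62% |
| Group-by-time, five levels | 54% | 71% | 92% |
| Adjusted post-operative average | 98% | 98% | 99.6% |

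At rho = 0.5 the four-level group term has 88% and the adjusted 3-year contrast about 82%.

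**Step 5. Power for a late difference** (assumed 0, 0, 0, 0.25, 0.5 SD at pre-op, 6 months, 1, 2 and 3 years; rho = 0.5; n = 50).
- Adjusted average: the effect is (0 + 0 + 0.25 + 0.5)/4 = 0.1875, and 0.1875/0.122 = 1.53, giving 33%.
- Group-by-time: the sum of squared deviations is 0.3125 - 5 x 0.15^2 = 0.20, so the noncentrality is again 10, giving 71%.
- Adjusted 3-year contrast: about 82%, as in Step 4.

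**Step 6. Error under the remedy, no instrument differing.** With the other four tested only after a significant primary, the chance of any false claim is 5.0%. Without that condition, a primary at 0.05 plus Holm on four would give 1 - 0.95 x 0.9875^4 = 9.7% at r = 0.

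**The case against.** The best defence is that the plan never states a superiority hypothesis, nor that one significant instrument is enough for a claim. Further, five scores from the same patient will be correlated, so the 23% end is unlikely. Both points are fair. The documents do not show an intention to claim on whichever instrument succeeds; they only leave that possible. Even at correlation 0.9, though, the rate is about twice nominal, and nothing marks the p-values as exploratory.

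Three stronger readings are tempting and are not supported.

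- **That the planned ANOVAs dilute the effect and lack power.** The 0.8d result holds only if pre-op is a level, and the 2 x 4 label leaves that unsettled. With four post-operative levels the group term has 88% power, not 72%, at rho = 0.5. Even with five levels, the better of the two terms has 85%, 72% and 92% across rho = 0.3, 0.5 and 0.7.
- **That the adjusted post-operative average is always the better contrast.** This is true for a steady difference. For the late pattern in Step 5 it has 33% against 71% for group-by-time. The background section mentions longevity, and no section says what shape of effect is expected.
- **That outcomes have already been examined by implant.** Design & Procedures says "We will ask subjects permission to use these questionnaires that have been collected from them since their randomized TAR surgery". Routine collection is not review by arm, so this does not contradict the no-monitoring statement. Whether those choosing the primary have seen results by implant is a question to answer, not a finding.

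**Conclusion.** The concern stands as an error-rate problem: five unranked instruments, one unadjusted threshold, and no deciding term. The false-positive chance is 10.2% to 22.6% for the group tests alone, given equal correlation from 0.9 down to 0 and one score per instrument. It is about 20% to 41% if group-by-time may also count in a five-visit layout. The correlation is an assumption, because the documents give none.

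The power figures illustrate why the contrast must be named. They do not show that the plan is underpowered, since they rest on complete data, an assumed effect size and shape, and an unresolved layout. The data remain usable, so this is a change that should be made rather than a fatal flaw.

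**What to change.** Amend Data Analysis & Statistical Considerations before the final analysis, and before anyone making the choice has seen outcomes by implant. State in the amendment whether that condition was met.

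1. **Primary instrument.** Name one. The choice is for the investigators. FADI is missing from the standard-of-care questionnaire list, so check its completeness, pooled over implants, before choosing it.
2. **Implant contrast.** Name one, adjusted for the pre-op value and tested at two-sided 0.05. Use the average over the 6-month to 3-year visits if a steady difference is expected, or one named visit such as 3 years if a late one is. Record the reason.
3. **Other four instruments.** Test the same contrast on them only if the primary is significant, with Holm within the four. Otherwise report estimates with 95% confidence intervals and no significance claim.
4. **Remaining tests.** Report the ANOVA group and group-by-time terms and the Tukey comparisons as descriptive, not as routes to a claim. Reconcile the 2 x 4 label with the five listed time points.

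This changes wording only, with no new visits or data. It has two costs. The other four instruments can no longer support a claim at an unadjusted 0.05. The choice of contrast is also a trade-off at rho = 0.5 and 50 per arm: the average falls to 33% power for the assumed late difference, while the 3-year contrast has about 82% against 98% for a steady one.

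Holm across all five instruments would avoid ranking them, but its first step is 0.05/5 = 0.01. A contrast with 80% power at 0.05 then has Phi(1.960 + 0.842 - 2.576) = 59%. Naming one primary spares the primary that loss.
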